7.2. General considerations of date analyses

7.2.1. General Statistical methods

SAS 9.4 software is adopted for Statistical analysis. Two-sided test is adopted for all Statistical tests. If the P value is less than 0.05, the tested difference will be considered "Statistically significant" (unless otherwise specified).

Descriptive analysis: Sort out and summarize a large number of data obtained from the survey to find out the internal law of these data - centralized trend and decentralized trend. Single factor analysis is mainly carried out with the help of statistics represented by various data, such as mean and percentage.

7.2.2. Statistical inference method

- The description of quantitative indicators includes the calculation of the mean, standard deviation, median, minimum value, maximum value, lower quartile (Q1), upper quartile (Q3), as well as the number and percentage of various types of classification indicators.
- In the comparison of the general conditions between the two groups, appropriate methods shall be adopted for analysis according to the type of indicators. The group t-test or Wilcoxon rank sum test is used for the comparison of quantitative data between two groups; Chi-square test or exact probability method is used for classification data; Wilcoxon rank sum test or CMH test is used for hierarchical data.
- The report is mainly expressed in tables: The tables are self-evident, that is, they have table titles, table notes and number of cases.

8. Data handling conventions

Data conversion:

Age (years) = (date of signing of informed consent form - date of birth + 1) / 365.25, rounded down.

Drug-related definitions are: definitely related, probably related, and possibly related.

Missing date: Since it is survival analysis data, it does not need to be filled. Missing text-type data is displayed as "" in the list. Numeric data is missing from the list with "." to display. If the data is recorded as "not applicable"/"NA" and "unable to assess"/"NK", the data will be displayed as raw records when described in the inventory, and processed as missing data for Statistical analysis.

Outlier: In general, all assay results will be used for Statistical analysis. If there is a clear outlier caused by special reasons and affects the Statistical analysis, it is missing and marked in the

Statistical analysis results / report.

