10.2 Data record

In accordance with the guidelines for completing the case report form, the investigators shall ensure the accuracy, completeness and timeliness of the recorded data, and ensure the response to data queries. The investigators shall verify the data that are significantly higher than or beyond the range of clinical acceptance, and make necessary explanations.

In modifying the data during filling in, the investigators shall indicate the reason for modification in the popped-up eCRF dialog box. Any modification by investigators will leave traces to ensure the authenticity of the data. For the questions in the CRF, the data administrator will generate a data query form and send a query to the investigators through the electronic data management system. The investigators shall give and return the answer as soon as possible.

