4.1. Design overview

This trial is a prospective, randomized, multicenter, open-label, parallel-arm clinical study, using the Logrank method to compare the difference of 1-year relapse free survival between the two groups. Enrollment was completed by 12 sites using competitive enrollment. The whole observation period is 1 year for this trial. Eligible patients who sign the informed consent form will be randomly divided into FK506 Group or MMF Group at the ratio of 1:1. Both groups follow the "clinical trial flow chart" in operation.

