7.1. Analysis data set

Full analysis set (FAS): It refers to the set of eligible cases and drop-off cases. The cases are required to have evaluation data after at least one treatment, but excluding the eliminated cases. Per-protocol set (PPS): It refers to the set of cases that meet the inclusion criteria, do not meet the exclusion criteria and complete the treatment plan, that is, the analysis of cases that meet the trial protocol, have good compliance and complete the specified content in CRF (PP analysis).

Safety set (SS): It refers to the actual data with safety index records after receipt of at least one treatment. The missed safety values shall not be carried forward. It includes some eliminated cases that can be evaluated, such as those whose age exceeds the inclusion criteria, but excludes those whose safety judgment cannot be made due to the use of banned drugs. For the incidence of adverse reactions, the number of cases in the safety set is used as the denominator.

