8.1.6. Safety analysis

Safety analysis mainly adopts safety set. All adverse events are coded by MedDRA 20.0 to describe the total number and incidence of adverse events (including serious adverse events), and the

frequency table is used to describe the frequency, severity of each adverse event and its relationship with the treatment. Adverse events relevant (related, probably related, and possibly related) to this research treatment are described and listed separately. Other safety indicators will also be described and summarized. The laboratory changes with clinical significance will be counted as AE.

9. Statistical analysis results

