9.4.2.9. Serum liver function and fasting blood glucose

Table 41. Change in glutamyl transpeptidase (GT) from baseline at each visit

Table 42. Change in alanine aminotransferase (ALT) from baseline at each visit

Table 43. Change in aspartate aminotransferase (AST) from baseline at each visit

Table 44. Change in lactate dehydrogenase from baseline at each visit

Table 45. Change in total bilirubin from baseline at each visit

Table 46. Change in direct bilirubin from baseline at each visit

Table 47. Change in alkaline phosphatase from baseline at each visit

Table 48. Change in total protein from baseline at each visit

Table 49. Change in globulin from baseline at each visit

Table 50. Change in fasting blood glucose from baseline at each visit

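### The SAP makes a value's effect on the analysis a condition for setting an outlier to missing, without defining the other conditions or exempting safety assays

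*SAP*

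**What the plan says.** The outlier convention in SAP section 8 has two parts. The default is: "In general, all assay results will be used for Statistical analysis". The exception follows: "If there is a clear outlier caused by special reasons and affects the Statistical analysis, it is missing and marked in the" statistical results or report. A value is therefore set to missing only if it is a clear outlier, has special reasons behind it, and also affects the analysis. The removal is then marked.

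Other text bears on how this rule works:

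- **Design (SAP 4.1):** "This trial is a prospective, randomized, multicenter, open-label, parallel-arm clinical study". Neither document describes a data review masked to arm.
- **Missing safety data (SAP 7.1):** "The missed safety values shall not be carried forward".
- **Laboratory tables (SAP 9.4.2):** eGFR, creatinine, liver enzymes, blood counts and urine protein are summarised by visit and as change from baseline, for example "Table 42. Change in alanine aminotransferase (ALT) from baseline at each visit". The template (Table 23) gives mean, median, quartiles, minimum, maximum and P-values.
- **Adverse events (SAP 8.1.6):** "The laboratory changes with clinical significance will be counted as AE".
- **Data checking (Protocol 10.2):** "The investigators shall verify the data that are significantly higher than or beyond the range of clinical acceptance, and make necessary explanations". The protocol has no rule for deleting outliers.

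**The concern.** Whether a measurement is valid depends on how it was obtained. What it does to a comparison is not evidence either way. Once effect on the analysis becomes a test for removal, somebody has to look at the analysis with and without the value before deciding. That lets the result influence the data set.

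The exposure is greatest for laboratory data, where an extreme value may be the finding. Renal function is both a secondary outcome and a safety outcome. Protocol 8.1.1 lists kidney injury as very common with tacrolimus, while the protocol's Background describes mycophenolate as free of nephrotoxicity. Genuine extremes may therefore fall unevenly between the arms, and a discretionary removal rule need not be neutral between them.

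**Working it through.** The plan gives no figure on this point, so there is none to reproduce. The check compares the rule with what a sound rule would do, then illustrates the possible size.

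**1. The rule by type of value.** Take an extreme value for which some special reason has been accepted.

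| Value | Affects the analysis | Does not affect it | Sound handling |
|---|---|---|---|
| Recording, sample or assay error | Set to missing | Kept | Exclude in both cases |
| Valid measurement | Set to missing, if the reason counts as special | Kept | Keep in both cases |

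The effect condition decides between the columns, although validity differs only between the rows. Only the special-reasons condition could separate the rows, and the SAP does not define it. It could mean a mislabelled tube. It could also be read to cover an intercurrent infection or high drug exposure, where the value is real.

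**2. What the SAP leaves open.** It does not define a clear outlier, special reasons, or what counts as affecting the analysis. It does not say who decides, when, or with what knowledge of the arm. It does not require the analysis with the value retained. One laboratory value also feeds several analyses (visit summary, change from baseline, FAS and PPS). The SAP does not say which of these must be affected, or whether the value then becomes missing in all of them.

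**3. What happens to a removed value.** It is not carried forward in the safety set (SAP 7.1), so it leaves a gap. Removing the single most extreme value always changes the reported minimum or maximum.

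**4. Size of a shift in the mean (illustrative).** Assumptions: one value per child in an arm of 135 (the planned arm size), mean eGFR 115, removed values of 50. The 115 and the 50 are not document figures.

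- One removed: (135 × 115 − 50)/134 = 15,475/134 = 115.49, a rise of 0.49.
- Three removed: (135 × 115 − 150)/132 = 15,375/132 = 116.48, a rise of 1.48.

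The mean moves little. The tails and the extremes move more.

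**5. Effect on a test (worst case).** Simulation with 115 per arm (about 135 × 0.85 = 114.75), no true difference, a pooled t-test at the SAP's two-sided 0.05 level (critical value 1.97) and 6,000 replicates per row. If the first test is not significant, the highest values of one arm may be dropped whenever that makes it significant.

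| Assumed distribution | Most values dropped | Type I error, all values | Type I error, after dropping |
|---|---|---|---|
| Normal | 1 | 5.1% | 8.1% |
| Normal | 3 | 5.0% | 14.9% |
| Lognormal, log-SD 0.5 | 1 | 5.4% | 10.5% |
| Lognormal, log-SD 0.5 | 3 | 5.3% | 23.5% |
| Lognormal, log-SD 1 | 1 | 4.7% | 11.6% |
| Lognormal, log-SD 1 | 3 | 4.7% | 32.0% |

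This shows what an effect-dependent rule could do if the special-reasons condition did not restrain it. It does not predict how the rule would be used.

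**The case against.** The strongest defence is that the effect condition narrows the exception. All results are used by default, effect alone never permits removal, and special reasons reads most naturally as an identified extraneous cause. Each removal is marked. Investigators must verify and explain out-of-range data, and eCRF changes leave a trace (Protocol 10.2). Clinically significant laboratory changes count as adverse events, and normal-to-abnormal results are listed by subject (SAP Tables 121-125). The SAP already provides medians, quartiles and Wilcoxon tests.

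Much of this stands, and it limits the point. It does not rescue the condition itself. Narrowing by effect on the result is the wrong way to narrow, and an undefined companion condition gives little protection. Marking discloses a removal but not what it did to the result. The adverse event route depends on judgement in an open-label trial, and Protocol 8.3 limits the adverse events collected to endpoint events, drug-related events and serious events. The SAP leaves the choice between t-test and Wilcoxon open.

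A reader might infer four stronger things that the documents do not support:

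- **Removal happens after the arms have been compared.** The SAP gives no timing, so the fault is that timing is unspecified.
- **Each removal deletes an abnormality from the shift tables.** Those tables (template in SAP 9.5.3, Table 71) compare only before treatment with Day 364±7, so an intermediate visit does not enter them. They classify clinical judgement and have a Missing category. The SAP does not say whether blanking a number also blanks that judgement.
- **The bias runs towards no harm.** The rule applies to high and low values in both arms, so either direction is possible. The simulation shows false positives, not hidden harm.
- **The primary result is compromised.** It is time to an adjudicated relapse (SAP 8.1.2 and 8.1.3). It would be touched only if a urine protein value that defines a relapse were treated as an outlier.

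**Conclusion.** The point holds as a defect in a stated rule, limited to secondary and safety laboratory summaries and their between-arm tests. Making effect on the analysis a condition for removal is unsound. The undefined terms, the absence of a named decider, timing or masking, and the lack of an exemption for safety assays leave it largely unrestrained. The possible bias is in either direction.

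Its size cannot be fixed from the documents. On the assumed values the shift in a mean is small, 0.49 for one removal and 1.48 for three. The possible effect on a significance test is larger: 8-12% type I error with one selective removal and 15-32% with up to three, under the assumed distributions and worst-case use. Adverse event counts are partly protected, the effect on shift tables is uncertain, and the primary analysis is largely unaffected. The rule should be changed, but it does not threaten the trial's main conclusion.

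**What to change.** Delete the condition about affecting the analysis and replace the convention in SAP section 8 with wording to this effect:

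- A value is set to missing only if it is a documented recording, sample or assay error, whatever its effect on any result.
- The decision is made before database lock, by named roles without access to the treatment code, drawing on the verification of out-of-range data in Protocol 10.2. Each exclusion is listed with its reason.
- All other values, including every valid safety value, stay in the main analysis. Suspected outliers are handled with the Wilcoxon test already provided for, or with a sensitivity analysis.
- The text states how an excluded value appears in the shift tables and subject listings.

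The cost is SAP wording plus a small amount of extra review and analysis work. Design, sample size and data collection do not change.

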8.1. Content of Statistical analysis

8.1.1. Basic value equilibrium analysis

The demographic characteristics, general conditions and baseline conditions (basic value indicators) of the two groups are analyzed to measure the comparability of the two groups. Group t-test or Wilcoxon rank sum test is used for measurement data; Wilcoxon rank sum test is used for classification or grade data; χ^2 test or Fisher test is used for classification data.

8.1.2. Effectiveness analysis

All effectiveness analysis/global indicators will be based on ITT principles, and FAS is adopted, for only the adjudicated endpoint events. The investigators are required to report all the potential endpoint events in eCRF.

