7.2.4 Relapse criteria

For 3 consecutive days, morning urinary protein changes from negative to (+++) or (++++) , or 24hr urinary protein quantification \geq 50 mg/kg, or urinary protein/creatinine (mg/mg) \geq 2.0.

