4.3. Research plan

4.4. Clinical trial flow chart

Clinical trial flow chart

Items	Screening and enrollment period		Treatment and follow-up period							
	Screen (V0)	Visit 1 (V1)	Visit 2 (V2)	Visit 3 (V3)	Visit 4 (V4)	Visit 5 (V5)	Visit 6 (V6)	Visit 7 (V7)	Visit 8 (V8)	Visit 9 (V9)
Follow-up week	Day -30 - 0	Included	Day 7	Day 28	Day 56	Day 112	Day 168	Day 224	Day 280	Day 364
Sign the informed consent gorm	✓									
Inclusion/exclusion criteria		✓								

Stop the original immunosuppressants after 2 weeks	\$	\$								
Randomized		√								
General data	√									
Medical history (course of disease, frequency of relapses in 1 year and 6 months before enrollment, steroid dosage)	√									
Vital signs	√	√	√	√	√	√	√	√	√	√
Height and weight	√	√	√	√	√	√	√	√	√	√
Physical examination	√	◎	√	√	√	√	√	√	√	√
Blood routine examination	√	◎	√	√	√	√	√	√	√	√
Urine routine examination	√	◎	√	√	√	√	√	√	√	√

Fasting blood glucose	√		√	√	√	√	√	√	√	√	√
Serum liver function	√	◎	√	√	√	√	√	√	√	√	√
Blood lipid	√	◎	√	√	√	√	√	√	√	√	√
Serum renal function	√	◎	√	√	√	√	√	√	√	√	√
Blood EBV-DNA, and CMV antibody	√										√
24hr urinary protein (>3 years old)	√	◎	√	√	√	√	√	√	√	√	√
Urinary protein / creatinine	√	◎	√	√	√	√	√	√	√	√	√
eGFR	√	◎	√	√	√	√	√	√	√	√	√
Tacrolimus concentration in plasma			√	√	√	√	√	√			√
Mycophenolic acid concentration in plasma			√					√			

Chest X-ray	√									√
ECG	√									√
Markers of hepatitis B and hepatitis C virus	√									
Examination of Mycobacterium tuberculosis and fungi	√									
Biological samples of blood and urine	√						√			√
Drug distribution and measurement		√	√	√	√	√	√	√	√	√
Guidance on the administration of test drug		√	√	√	√	√	√	√	√	√
Clinical efficacy (relapse or no)			√	√	√	√	√	√	√	√

Concomitant medication	√	√	√	√	√	√	√	√	√	√
Adverse event			√	√	√	√	√	√	√	√
Record case report form	√	√	√	√	√	√	√	√	√	√

Remarks:

1. Liver function: ALT, TBIL, ALB; Renal function: creatinine, blood urea nitrogen, uric acid, Cystatin C;
2. Blood lipids: Triglycerides, cholesterol; Urinary protein / creatinine: morning urine; Markers of hepatitis B and hepatitis C virus: HBsAg, HBeAg, HBcAb, HCV;
3. Mycobacterium tuberculosis examination: T-sport; Fungal examination: fungal G test or other; Estimated glomerular filtration rate: eGFR = $K \times \text{height (cm)} / \text{serum creatinine (mg/dL)}$ (see Appendix);
4. Visit time window: ± 3 days for visit 2, and ± 7 days for other visits;

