6.2.4. Relapse criteria

For 3 consecutive days, morning urinary protein changes from negative to (++) or (+++), or 24hr urinary protein quantification ≥ 50 mg/kg, or urinary protein/creatinine (mg/mg) ≥ 2.0 .

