8.1.3. Primary efficacy analysis

Logrank test is used for the analysis of relapse-free survival rate which is then used as a covariate for stratification by Sites. HR and its 95% confidence interval (CI) are calculated with Cox proportional hazard model to estimate the efficacy, the confidence interval is applied to verify the superiority of the experimental group and the control group, with a cut-off value of 1 (risk ratio). The model incorporates the same covariate as the Logrank test for fitting, and the definition method of covariates is also the same as that in the Logrank test. The Kaplan-Meier curve of relapse-free survival is drawn by treatment groups. The 1-year relapse-free survival rate and its confidence interval are then calculated.

Calculation rules for the main efficacy indicators:

- If relapse occurred within 9 visits (within 364 ± 7 days) or unscheduled visits within 365 days of randomization, defined as the occurrence of endpoint events. Time of relapse = date of relapse - Random date + 1, calculated by days.
- If the visit stipulated in the protocol was not completed within 9 visits (within 364 ± 7 days) due to loss of follow-up midway or withdrawal or other reasons, it is defined as censoring. Time of

censoring = date of withdrawal - random date + 1, calculated by days.

- If the visit stipulated in the protocol was not completed within 9 visits (within 364 ± 7 days) due to death in the trial, it is defined as censoring. Time of censoring = Death date - random date + 1, calculated by days.
- If the visit stipulated in the protocol was completed and there is no relapse within 9 visits (within 364 ± 7 days), it is defined as censoring. Time of censoring = date of visit 9 (within 364 ± 7 days) - random date + 1, calculated by days.

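### Efficacy analyses are limited to adjudicated events, but no adjudication step is described and SAP 8.1.3 counts an in-window relapse without one, so the rule for the primary event is unsettled in an open-label trial

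*SAP*

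**What the plan says.** Protocol 11.3.2 and SAP 8.1.2 carry the same sentence: for all effectiveness analyses, "FAS is adopted, for only the adjudicated endpoint events". The next sentence reads: "The investigators are required to report all the potential endpoint events in eCRF". Site reports are thus treated as candidates for the endpoint.

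SAP 8.1.3 gives the calculation rules for the primary endpoint. A relapse within nine visits (364±7 days), or at "unscheduled visits within 365 days of randomization, defined as the occurrence of endpoint events", is dated by the date of relapse. No confirmation is required.

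On design, SAP 4.1 states: "This trial is a prospective, randomized, multicenter, open-label, parallel-arm clinical study". The flow chart (Protocol 1.3, SAP 4.4) has relapse recorded as yes or no at every visit from Visit 2.

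On criteria, Protocol 7.2.4 reads "For 3 consecutive days, morning urinary protein changes from negative to (+++) or" (++++). SAP 6.2.4 reads "For 3 consecutive days, morning urinary protein changes from negative to (++) or" (+++). The other two limbs agree: 24-hour protein of at least 50 mg/kg, or protein/creatinine of at least 2.0.

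**The concern.** One sentence makes adjudication a condition for entering any efficacy analysis. The detailed rule for the primary endpoint omits it, and nothing in between says how a potential event becomes an adjudicated one. Two programmers, one starting from SAP 8.1.2 and the other from SAP 8.1.3, could build different primary event sets, and the plan does not say which section governs.

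Two routes remain open. Either the site's yes/no call, made with knowledge of treatment, is the endpoint, or someone decides after reporting which relapses count. Relapse is the only event in the primary analysis. Confirming relapses unevenly between arms would therefore bias the log-rank test and the hazard ratio directly.

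**Working it through.** **1. The plan's own figure.** With exponential hazards, HR = ln 0.70 / ln 0.56 = 0.3567/0.5798 = 0.6151, as in Protocol Appendix 4. With 2 years' uniform accrual and 3 years in total, the event probability is 1 − (e^(−h) − e^(−3h))/(2h). This gives 0.6685 × 114 + 0.4995 × 115 = 76.2 + 57.4, or about 133.7 events against the stated 133.8. Then 229/0.85 = 269.4, rounded up to 270. The sample-size arithmetic reproduces, so the point concerns which relapses become events.

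**2. The passages side by side.**

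| Question | Protocol 11.3.2 / SAP 8.1.2 | SAP 8.1.3 |
|---|---|---|
| What counts? | Adjudicated events only | Relapse in the window |
| Status of a site report | Potential event | Not distinguished |
| Who confirms, and masked to arm? | Not stated | No confirmation |
| Reported but unconfirmed relapse | Excluded by implication | Counted |

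The listing shells (SAP Tables 117–120) have no adjudication field. Table 117 holds relapse dates and a description, but no fields for the qualifying urine values.

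**3. How much uneven confirmation would matter.** The documents give no misclassification rate, so the following is an assumption shown over a range. Inputs: 135 per arm (Protocol 3.3.2); one-year follow-up (SAP 8.1.3); no true difference, with both arms relapse-free at S = 0.56, 0.63 or 0.70 (the two planning values and their midpoint). A fraction q of one arm's relapses is not confirmed, and those children are carried on as relapse-free.

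Closed form without loss to follow-up: p = 1 − S; p′ = p(1 − q); apparent HR = ln(1 − p′)/ln(1 − p); D = 135(p + p′); z = √(D/4) × |ln HR|; rejection = Φ(z − 1.96) + Φ(−z − 1.96).

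For S = 0.56 and q = 10%: p′ = 0.396; HR = ln 0.604 / ln 0.56 = 0.8695; D = 135 × 0.836 = 112.9; z = 5.31 × 0.140 = 0.742; rejection = 0.115.

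A simulation (exponential relapse times, 15% exponential loss over the year, 10,000 trials per cell) gives the second figure in each cell:

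| S, both arms | q = 5% | q = 10% | q = 20% |
|---|---|---|---|
| 0.56 | 6.6% / 6.1% | 11.5% / 10.5% | 32.3% / 29.5% |
| 0.63 | 6.2% / 5.6% | 9.8% / 9.4% | 25.6% / 23.7% |
| 0.70 | 5.9% / 5.6% | 8.5% / 8.2% | 20.1% / 18.9% |

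At q = 0 the simulated error is 4.7–5.2%. Separate runs of 4,000 trials per cell gave 8.3–11.2% at q = 10% and 18–30% at q = 20%. Rounded over these calculations with loss, the error is about 6–7%, 9–11% and 18–29%, with each end good to about one percentage point.

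**4. In children.** Before loss, 10% of one arm's relapses is 135 × 0.44 × 0.10 = 5.9 at S = 0.56, and 135 × 0.30 × 0.10 = 4.1 at S = 0.70. Four to six one-sided decisions are enough to roughly double the nominal error.

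**The case against.** The strongest reply is that relapse is defined by laboratory values. SAP 8.1.3 uses a term defined in SAP 6.2.4, within a stated window, and it can be carried out as written. SAP 8.1.2 is a general sentence. In a translated text, its qualifier may mean only that an event was judged to meet the criteria. The two sections could then be read together, leaving an undefined term. Other controls also bear on ascertainment: local laboratory assessment where a potential endpoint arises (Protocol 8.3), source-data checks by the monitor (9.2), and cross-laboratory comparison of urinary protein and creatinine (9.1 and Appendix 3).

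Much of this stands. The thresholds do limit discretion. However, the dipstick limb has different grades in the two documents, so whoever applies the criteria has two versions to choose from. The other controls address data quality; none is an arm-masked decision on whether a relapse counts. The benign reading of the qualifier is possible, but the text does not establish it.

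Three stronger readings are tempting, and the documents do not support them:

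- A reader might infer that no event can be analysed. SAP 8.1.3 is specific and workable, so that does not follow.
- A reader might infer that the endpoint is pure unblinded judgement, or that any relapse at all counts. The thresholds and the window rule that out.
- A reader might infer that nothing would reveal a dropped event. Tables 118–120 show by group whether a relapse occurred and, separately, whether it was an endpoint event, and Table 117 lists the relapses. An uncounted relapse could be seen there. What is not planned is a reason for the exclusion or a count by arm.

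**Conclusion.** The point holds in this form: both documents claim an event-confirmation safeguard that neither describes, and the operative rule in SAP 8.1.3 does without it. The primary event could be the site's call or a later selection among reported relapses, and the conflicting dipstick grades widen that latitude.

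The error rates of about 6–7%, 9–11% and 18–29% rest on assumed one-arm non-confirmation of 5%, 10% and 20%. They cover under-confirmation only; over-calling is not modelled. They are not evidence that such bias has occurred, and at 5% or below the inflation is small. The conclusion on the text does not depend on them. It rests on the documents as supplied; an adjudication charter held elsewhere would need to be cited and described.

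**What to change.** Before the primary events are derived:

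1. Reconcile the relapse criteria in Protocol 7.2.4 and SAP 6.2.4.
2. Delete the adjudication qualifier from Protocol 11.3.2 and SAP 8.1.2, and make SAP 8.1.3 the single event rule.
3. Derive the primary event and its date by program, with the arm masked, from the dated urine values recorded for each reported potential relapse. Use the scheduled urine results only to flag possible unreported relapses, because visits weeks apart cannot by themselves establish three consecutive days.
4. Fix in advance, identically for both arms, how a reported relapse with incomplete daily values is counted. Keep it as an event in the primary analysis unless recorded values contradict the criteria. Otherwise missing values would themselves cause under-confirmation.
5. Report investigator-called relapse as a sensitivity analysis, and tabulate reported against criteria-confirmed relapses by arm.

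The cost is wording changes in both documents, one derivation program, and site entry of the dated urine values behind each relapse. No committee, extra visit or larger sample is needed.
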